3.4 Co-enrolment Guidance

Participants cannot participate in the PETRA trial if they are currently enrolled in any other Clinical Trial of an Investigational Medicinal Product (CTIMP). They must also not be enrolled if they have participated in a CTIMP in the preceding 3 months.

3.5 Screening Procedures and Informed Consent

Patients will be provided with a Participant Information Sheet (PIS) and given sufficient time to read it fully (a minimum of 24 hours). Following a discussion with a medically qualified investigator or suitable trained and authorised delegate, any questions will be satisfactorily answered and if the participant is willing and has the capacity to consent and wishes to participate, informed consent will be obtained. This could be a paper consent form or e-consent and will be signed by a delegated member of site staff.

The local PI or clinical delegate will also review participants who have any cautions for pregabalin, for example renal impairment, co-existing chronic obstructive airways disease, and co-prescription of opioids, benzodiazepines, or z-drugs, and then decide if participants should be randomised. This will be done, when necessary, in consultation with the participant's GP.

If a patient has capacity and is willing to provide verbal consent, but is physically unable to sign the consent form, a witness independent of the trial team will be identified and asked to sign the witness signature field in the consent form, to attest to the patient's verbal consent to participate.

3.5.1 Process of informed consent

A copy of the approved consent form is available from the trial team.

Written informed consent to enter and be randomised into the trial must be obtained from participants, if appropriate, after explanation of the aims, methods, benefits, and potential hazards of the trial and **BEFORE** any trial-specific procedures are performed. The only procedures that may be performed in advance of written informed consent being obtained are those that would be performed on all patients as usual standard of care.

It must be made completely and unambiguously clear that the participant is free to refuse to participate in all or any aspect of the trial, at any time and for any reason, without incurring any penalty or affecting their treatment.

Signed consent forms must be kept by the investigator and a copy given to the participant or family. The investigator and participant will have access to a copy regardless of method of consent used (paper or electronic). The consent process should be documented in the participants medical records. With the consent of the participant, a letter should be sent to the general practitioner informing him/her of the trial and the participant's involvement in it.

3.5.2 Consent procedure for the nested qualitative study

At the beginning of the study, trial participants will be asked to provide consent to participate in an optional interview conducted online after the 12-week visit. We will include participants from recruiting regions and maintain the blinding. We anticipate including at least 25 participants who have completed the week 12 visit and at least 10 participants who stopped study medication before 12 weeks (numbers depending upon data saturation).

3.5.3 Screening Visit

Once informed consent is obtained study assessments must be performed as detailed in Participant Timeline (section 5.2)

4 Trial treatments / Intervention

4.1 Introduction

Participants will be randomised with a 1:1 ratio to placebo or pregabalin (starting with 50mg and increasing to the recommended dose of 200mg) using a flexible dosing strategy that will mimic usual care to enhance retention.

4.2 Arm A: Active drug

4.2.1 Product

Pregabalin in 50mg tablets (sourced from any manufacturer with a marketing authorisation in the UK).

4.2.2 Regulatory Status

Pregabalin is a licensed drug and indicated for generalised anxiety disorder.

4.2.3 Dispensing & Storage

The Pharmacy Trials Unit at Bristol Royal Infirmary will act as the central pharmacy and will be responsible for dispensing and storage of pregabalin. More information regarding the distribution to participants can be found in the IMP Management Plan.

4.2.4 Dose Modifications, Interruptions and Discontinuations

(See also Section 4.7 for treatment discontinuation)

The study will allow flexibility in the dose to mimic clinical practice and to increase the acceptability of the intervention if people experience adverse effects. PPI input and prescribing experience indicate that there is a great deal of variation in the experience of adverse effects and in their tolerability. Clinical experience also indicates that increasing pregabalin slowly also increases the tolerability of any adverse effects. Allowing flexibility will increase retention of participants.

Participants will be given clear instructions to titrate the dose starting:

- Day 1-4 one tablet a day (50mg),
- Day 5-9 two tablets a day (100mg)
- Day 10-14 three tablets a day (150mg)
- Day 15 onwards four tablets a day (200mg)

The participants will be advised to stop increasing the medication at the point they find it is satisfactorily effective, or if they experience adverse effects which are not tolerable. Participants will be advised to contact their research team if any concerns that insufficient supply to last between study visits to enable timely delivery of their next medication supply. The medication instructions PIS will provide more information and contact details for the research team.

At the PI discretion, study medication can be increased beyond the recommended 4 tablets a day (200mg) to either 5 tablets a day (250mg) or 6 tablets a day (300mg). Participants should try the recommended dose of 200mg for a minimum of 2 weeks before the PI considers increasing their dose. If a PI is increasing a participant's dose above 200mg then it will be recorded in the study database.

For participants that increase their dose above the recommended dose of 200mg the dose should be titrated as follows:

- Four tablets a day (200mg) for at least 2 weeks before a dose increase is considered
- Five tablets a day (250mg) for at least 2 weeks before a dose increase is considered
- Six tablets a day (300mg) – maximum dose

All participants will continue taking the study medication until the tapering period (see below) starts at the 26 week follow up assessment. The participants dose will be gradually reduced over the tapering period to minimise withdrawal side effects.

If a participant experiences intolerable side effects, the dosage may be decreased to the previous dose level at any time during the double-blind period and will be documented. The GP will be informed of any dose changes.

In cases where participants have missed doses, these should be reviewed and discussed by the investigator at the research site to advise on the best dosing plan to remain on trial medication. Participants who discontinue study medication will be invited to all follow up assessments. Once participants have discontinued study medication, they will not be able to re-commence.

4.3 Arm B: Placebo

4.3.1 Products

As this is a double-blind trial, participants in Arm B (placebo) will be given the same instructions as per Arm A (Active drug), described in section 4.2.

4.3.2 Regulatory Status

N/A

4.3.3 Dispensing & Storage

Pharmacy trials unit at Bristol Royal Infirmary will act as the central pharmacy and will be responsible for dispensing and storage of identical placebo. More information regarding the distribution to participants can be found in the IMP Management Plan.

4.3.4 Dose Modifications, Interruptions and Discontinuations

See section 4.2.4 for details.

4.4 Concomitant Care

The participants will continue with their usual care with their GP while they are in the study.

4.5 Overdose of Trial Medication

If someone takes an overdose of the trial medication, they should attend accident and emergency department as soon as possible. The clinician at the A&E can then decide if there needs to be emergency unblinding and will take any further action as required.

4.6 Unblinding

The unblinding of participants will be done by the central pharmacy who will notify the participant's GP of the allocation so that further treatment can be discussed. The research team will remain blind to this information.

4.6.1 Routine Unblinding

Routine unblinding will occur when the participant has discontinued trial medication, and has completed all interviews at the end of the 30-week trial participation period and all data has been entered into the database

4.6.2 Emergency Unblinding

Unblinding may occur for any participant experiencing a medical emergency for which the clinical management will be facilitated by the unblinding of the participants treatment allocation. All participants will be given a card with contact details for the trial team including emergency contact details for the central pharmacy for unblinding 24 hours a day, 7 days per week.

In the event of unblinding becoming necessary, the central pharmacy will provide unblinding 24-hour 7 days a week. The PI or delegate cannot overrule any decision made by a referring clinician. It is anticipated that in most instances, appropriate clinical management can proceed with the assumption that the participant has been treated with active IMP without needing to unblind the participant.

Detailed information regarding unblinding is provided in the PETRA Unblinding Plan.

4.6.3 Unblinding for the Submission of SUSAR reports

All SAEs that are related to the trial medication (i.e., SARs) and are suspected to be unexpected i.e., SUSARs, need to be submitted to the regulatory agencies within pre-specified timelines. When SAEs reports are received by the trial team, if the event is recorded as being a SUSAR then the following procedure will be used to unblind the SUSAR to determine if the participant was receiving active trial medication, and therefore, that the SUSAR needs onward reporting to the regulatory agencies:

- A member of the CCTU trial SUSAR Reporting Team will unblind the participant's trial treatment allocation via the central pharmacy.
- If the participant is revealed to the CCTU SUSAR Reporting team to be receiving active treatment, the CCTU trial SUSAR Reporting Team member will report the SUSAR via ICSR Submissions portal to the MHRA and REC as required.
- This information will not be forwarded to the UCL trial team or the sites. It will be kept in a separate file by the CCTU SUSAR reporting team.

4.7 Protocol Treatment Discontinuation

In consenting to the trial, participants are consenting to trial treatments, trial follow-up and data collection. However, an individual participant can stop treatment early or be stopped early for any of the following reasons:

1. Unacceptable treatment toxicity or adverse event
2. Any change in the participant's condition that in the clinician's opinion justifies the discontinuation of treatment
3. Withdrawal of consent for treatment by the participant
4. Significant deviation from the dosage regime
5. Pregnancy

If at any point in the trial, the PI is concerned about the clinical condition of a participant and decide they should be treated by their GP, we will withdraw that participant from the trial medication and ensure that they receive appropriate treatment outside the trial. The decision to withdraw will require a clinical judgement about the appropriateness of continuing with treatment.

As participation in the trial is entirely voluntary, the participant may choose to discontinue trial treatment at any time without penalty or loss of benefits to which they would otherwise be entitled.

All participants must be advised to taper the study medication and reduce the dose gradually if they want to stop the medication. Although not obliged to give a reason for discontinuing their trial treatment, a reasonable effort should be made to establish this reason, whilst remaining fully respectful of the participant's rights. If the participant chooses to discontinue the trial treatment, we will provide them with specific instructions for tapering that can be altered at the discretion of the PI and depending upon the number of tablets they are taking.

The recommended tapering regimen is as follows:

If participant is taking 4 tablets:

- 9 days on 3 tablets

- 9 days on 2 tablets
- 10 days on 1 tablet.

If taking 3 tablets:

- 14 days on 2 tablets
- 14 days on 1 tablet

If taking 2 tablets:

- 1 tablet for 14 days

If taking 1 tablet:

- Can stop straight away

If at the discretion of the PI the participant is taking a higher dose of 5 tablets (250mg) or 6 tablets (300mg) then the recommended tapering regimen is as follows:

If participant is taking 6 tablets:

- 5 days on 5 tablets
- 5 days on 4 tablets
- 6 days on 3 tablets
- 6 days on 2 tablets
- 6 days on 1 tablet.

If taking 5 tablets:

- 7 days on 4 tablets
- 7 days on 3 tablets
- 7 days on 2 tablets
- 7 days on 1 tablet.

Participants should remain in the trial for the purpose of follow-up and data analysis (unless the participant withdraws their consent from all stages of the trial). If a participant ceases follow-up early, refer to Section 5.4

Data on participants who stop follow-up early will be kept and included in analysis.

Tapering phase

After the 26 week follow up assessment is completed participants will be given instructions to taper the study medication over the following 28 days. There will then be a further follow up assessment 30 days after the tapering period has started that we have called the ~30-week assessment. The instructions given to participants will be:

If someone is taking 4 tablets: they will be advised to have 9 days on 3 tablets, 9 days on 2 tablets and 10 days on 1 tablet. If taking 3 tablets: 14 days on 2 tablets, 14 days on 1 tablet. If taking 2 tablets: 1 tablet for 14 days. If taking 1 tablet: can stop straight away.

4.8 Accountability & Unused Trial Medication

The study central pharmacist will be delegated oversight of IMP supplies. Full IMP Accountability records will be maintained at the pharmacy. The CCTU will request copies of accountability logs and confirmation of destruction/disposal or any expired/unused IMP.

Any unused medication should be disposed of upon discontinuation of trial medication via the following methods:

- Returned by participant to local pharmacy for disposal
- Returned to researcher at site for disposal (via local pharmacy or return to central pharmacy)
- Pre-paid envelopes may also be considered to allow participants to return trial medication directly to the central pharmacy (where necessary)

4.9 Adherence

The adherence to the study medication will be assessed at each follow up point. There is a structured assessment in the questionnaires at each follow up point.

5 Assessments & Follow-Up

5.1 Outcomes

We will collect outcome data by videolink or by phone/audio but on occasions will also use links to website questionnaires or in person interviews. This is to ensure that participants have a choice about the most convenient method for them.

5.1.1 Primary Outcome

Difference between anxiety symptoms (measured with GAD7 at 12 weeks post randomisation as a continuous score) (Spitzer *et al.*, 2006) between those participants who were allocated to receive placebo versus those who were allocated to pregabalin, accounting for the participant level baseline GAD7 score.

5.1.2 Secondary Outcomes

Anxiety and Depression

- Anxiety scores (GAD7) at week 3, week 6, week 26 and week 30.
- Dichotomised anxiety scores (present or absent based on a cut-off of GAD7 ≥ 10) at week 3, week 6, week 12, week 26 and week 30.
- Depressive scores (PHQ9) (Gilbody *et al.*, 2007) at week 3, week 6, week 12, week 26 and week 30.
- Panic symptoms (Spitzer, 1999)

Global Improvement & Quality of Life

- EQ5D5L (Herdman *et al.*, 2011) & SF-12 (Brazier and Roberts, 2004) at week 3, week 6, week 12, week 26 and week 30

Adherence

- Adherence to study medication will be assessed using a single item asking if they are still taking study medication and a 5-item scale used in the MIR and Cobalt studies. (Wiles *et al* 2013; Kessler *et al* 2018)

Withdrawal & Adverse Events

- Adverse effects of pregabalin and antidepressants – based on the Toronto scales for antidepressants (as used in GENPOD study (Crawford *et al.*, 2014)) with additional symptoms of pregabalin side effects (including waist circumference) and pregabalin withdrawal
- Withdrawal symptoms from pregabalin – these are included in the adverse effect scale above
- Stopping the study medication

Use of alternative anxiolytic methods

- Alcohol consumption (AUDIT PC) measured at every visit (Gómez *et al.*, 2005)
- Benzodiazepine use measured at every visit

Resource Use and Employment

- Primary care resource use (6 months pre and post randomisation)
- Antidepressant medication collected from primary care medical records (6 months pre and post randomisation)
- Self-reported health resource use (baseline and 26 weeks asking about previous 6 months) including psychological therapies.
- Self-reported social care resource use (baseline and 26 weeks asking about previous 6 months)
- Employment and time off work (baseline and 26 weeks asking about previous 6 months)

Cognitive Assessments

- Exploratory Assessments of reinforcement learning, working memory and general cognitive function (administered through a web browser using the Gorilla platform)

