Key Secondary Outcomes	
 • Anxiety symptom scores (GAD7) at all other follow up times (3, 6, 26, ~30 weeks) and GAD7 as a binary outcome (GAD7 ≥ 10) at follow up times (3, 6, 26, ~30 weeks). • Self-reported health and social care resource use, employment and time off work will be completed at 26 weeks (asking about the previous 6 months) using a bespoke health and social care Resource Use Questionnaire. • Medication prescriptions will be collected from primary care medical records covering 6 months pre and post randomisation. 
The following key secondary outcomes are repeated at all follow-up visits:
 
 • Depressive symptom scores using PHQ-9. • Self-reported global improvement, quality of life with SF-12 Health Survey and EQ-5D-5L. • Adverse effects of pregabalin and antidepressants adverse effects using scales from previous studies with additional items for pregabalin. • Adherence to study medication using a single item asking if they are still taking study medication and a 5-item scale used in the MIR and Cobalt studies. • Alcohol consumption using the AUDIT-PC. • Benzodiazepine use.

	After completion of the 26-week assessment and the taper period there will be a follow-up assessment 30 days after the 26-week assessment and we have called this the ~30 week follow up assessment. The comparison between the randomised groups will be double blind. Withdrawal symptoms that have been reported include agitation, irritability, insomnia, myalgia and palpitations and will be assessed using self-administered scales.
Nested Qualitative study	Some participants will be invited to a semi-structured interview that we have called the "6 th additional interview" in the PIS and this will explore acceptability of taking and prescribing pregabalin for anxiety, from the perspectives of trial participants and GPs.

Roles and responsibilities

These membership lists are correct at the time of writing; please see terms of reference documentation in the TMF for current lists.

Protocol contributors

Name	Affiliation	Role
[name]	DoP UCL	Chief Investigator
[name]	DoP UCL	Trial Manager
[name]	University of Bristol	Professor of Primary Care
[name]	University of Bristol	Professor of Epidemiology
[name]	Keele University	Professor of General Practice Research
[name]	UCL	Associate Professor in Psychiatric Epidemiology
[name]	UCL	Associate Professor in Statistics

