5.2 Participant Timeline

Figure 1. Participant Timeline

Visit Number	SCREENING	BASELINE					3	6	12	26	~30
		0	0 Randomisation	3	6	12					
Week	-t	0	0 Randomisation	3	6	12	26	~30			
Informed consent		X									
Pregnancy test		X									X
Randomisation/Treatment group allocation		X									
Sociodemographic (background) questionnaire	X										
GAD-7	X	X		X	X	X	X	X			
CIS-R		X									
History of anxiety and/or depression and treatment, smoking, negative childhood/adulthood experiences, events in past 6-months, social support		X									
AUDIT-PC				X	X	X	X	X			
PHQ-9		X		X	X	X	X	X			
SF-12 Health Survey		X		X	X	X	X	X			
EQ-5D-5L		X		X	X	X	X	X			
Medication adherence	X			X	X	X	X	X			
Adverse events/physical symptoms		X		X	X	X	X	X			
Questions about taking part in this research	X										
Global improvement		X		X	X	X	X	X			
Suicidal ideation		X		X	X	X	X	X			
Cognitive assessments		X		X		X					
Bespoke health and social care Resource Use Questionnaire		X						X			
Medication prescription (up to 7)			X	X	X	X	X	X			
Semi-structured interview with sub-sample of participants							X				
Semi-structured interview with up to 15 GPs											X

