7.6 Data Management

Data will be collected at the time-points indicated in the Participant Timeline (Section 5.1). Data will be entered under this PIN onto the central database. The database software provides a number of features to help maintain data quality, including maintaining an audit trail, allowing custom validations on data, allowing users to raise data query requests, and search facilities to identify validation failure and missing data.

Data collection, data entry, queries raised by a member of the PETRA trial team and database lock(s) will be conducted in line with the CCTU SOPs and trial-specific Data Management Plan.

The database will be password protected and only accessible to members of the PETRA trial team at UCL, Bristol and Keele; delegated site staff and external regulators if requested. Database users will only be granted permissions to use the database functionality appropriate to their role in the clinical trial.

Identification logs, screening logs and enrolment logs will be completed and held securely with access limited to trial staff that require the information.

All data will be handled in accordance with the Data Protection Act 2018, the EU General Data Protection Regulation (GDPR) 2016 (and subsequent updates and amendments).

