8.3 Statistical Considerations

8.3.1 Estimand Framework & Statistical Analysis Plan

Table 5. Estimand Framework

Characteristic of estimand	Definition and method of analysis
Population	Participants who have a diagnosis of generalised anxiety disorder, who have not responded to at least two antidepressant

	medications, who are currently still taking antidepressant medication, who are in the community, who agree to enter the trial and who do not fulfil exclusion criteria.
Treatment conditions	Pregabalin medication versus placebo in addition to care as usual
Endpoint	Natural log of the score on the Generalised Anxiety Disorder scale at 12 weeks post randomisation
Summary measure	Mean difference between natural log of the score on the Generalised Anxiety Disorder scale at 12 weeks post randomisation between those randomised to placebo versus those randomised to pregabalin (adjusting for baseline scores).
Intercurrent Events	
 i. Death before outcome While alive policy ii. Withdrawal from randomised medication (stays in trial) Treatment policy iii. Withdrawal from medication (leaves trial) While in trial policy iv. Increased use of alcohol Treatment policy v. Psychiatric admission Treatment policy vi. Commencement of psychological therapies Treatment policy

Statistical Analysis Plan

A separate Statistical Analysis Plan will be pre-specified which will be held within the Statistics Master File (SMF). It will contain following sections:

- I. Introduction
- II. Study Methods
- III. Statistical Principles
- IV. Trial Population
- V. Analysis of Primary and Secondary Outcomes (including statistical models and method of dealing with missingness)

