8.3.3 Statistical Methods – Outcomes

The primary analysis will be a generalised mixed model with identity link and Gaussian / mixed error structures, with log(e) GAD7 scores at 12 weeks as the outcome, accounting for baseline GAD7 scores using a repeated measures framework and also including minimisation factors used in the randomisation process. Natural logarithms will be used following our previous experience with the PANDA study(Lewis *et al.*, 2019) that suggested it was more efficient, and evidence that minimal clinically important differences for scales such as GAD fit a geometric model more closely. There will be two observations for each participant, the baseline and 12-week scores. These will be linked within a participant using a random intercept term. The model will be parameterised to identify baseline and post randomisation observation as one parameter, and random allocation as the second parameter. For the latter, all baseline measures will be coded as no treatment, and the post randomisation values will be classified as active or placebo. We will not make adjustments for repeated testing but will discuss the possibility that type 1 errors would have increased in the discussion.

Secondary analyses will choose the appropriate analogous generalised mixed model, for the outcome and account for the baseline measurement of the outcome. We will describe randomised groups at baseline. Summary statistics for continuous variables will be mean, median, SD, lower quartile, upper quartile and reported appropriately according to distribution. Summary statistics for binary and categorical variables will be n (%).

We will carry out supportive analyses including the minimisation variables as explanatory variables. We will also investigate baseline variables associated with missing outcome data for the primary outcome. We will carry out mediation analyses to examine the influence of missingness. All principal analyses will be complete case, intention to treat (defined as all patients randomised, analysed according to their randomised group regardless of treatment received). Although we will minimise missing data by trial conduct (building on the considerable experience and success of the team on previous studies) we will investigate the potential impact of missing data on the primary objective through threshold analyses which will impute a poor outcome for missing pregabalin patients while assuming an average outcome for missing control patients.

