8.3.6 Analysis Population and Missing Data

Outcomes will be analysed by means of Generalised Mixed Models without imputation of missing data. Measurements within individuals will be linked using a random intercept term. We will use two timepoints for the final analysis; baseline and primary timepoint at 12 weeks. An Intention-To-Treat (ITT) analysis will be carried out by randomisation group irrespective of medication compliance. The analysis population will consist of all those participants who were randomised. Mechanisms of missingness will be explored. The principal analyses will address a treatment strategy estimand, except death which will be while alive.

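### AUDIT-PC has no baseline mark in the Participant Timeline, although the outcome list says every visit and the secondary model needs a baseline value

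*Protocol*

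**What the plan says.** Four parts of the protocol bear on when AUDIT-PC is collected and how it is analysed.

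- **Outcome list (5.1.2):** "Alcohol consumption (AUDIT PC) measured at every visit". Read literally, this includes baseline.
- **Protocol summary, Key Secondary Outcomes:** AUDIT-PC is in a list introduced by "The following key secondary outcomes are repeated at all follow-up visits". This covers follow-up and does not state whether there is a baseline measurement.
- **Participant Timeline (5.2):** the row reads "AUDIT-PC X X X X X", five marks. Section 7.6 gives this table its authority: "Data will be collected at the time-points indicated in the Participant Timeline".
- **Secondary analysis (8.3.3):** secondary outcomes use a generalised mixed model analogous to the primary one and "account for the baseline measurement of the outcome".

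The primary model in 8.3.3 uses two observations per participant, baseline and 12 weeks, linked by a random intercept. Section 8.3.6 repeats that two-timepoint structure.

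**The concern.** The outcome list and the schedule disagree about baseline, and the analysis section depends on the version that the schedule leaves out. Staff working from the timeline would not administer AUDIT-PC before randomisation. The week 3 score cannot stand in for it, because it is measured after treatment has started and may itself be affected by treatment.

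This is not a detail that a separate statistical analysis plan can settle later. The analysis plan can choose another model, but it cannot recover a pre-randomisation value that was not taken. Each participant enrolled under the timeline as it stands is one more without that value.

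What is at stake is limited: the planned form of analysis, and some precision, for one secondary outcome.

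**Working it through.** **1. Count the marks in the Participant Timeline (5.2).**

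| Row | Screening | Baseline | Follow-up (3, 6, 12, 26, ~30) | Total |
|---|---|---|---|---|
| GAD-7 | 1 | 1 | 5 | 7 |
| PHQ-9 | 0 | 1 | 5 | 6 |
| SF-12 | 0 | 1 | 5 | 6 |
| EQ-5D-5L | 0 | 1 | 5 | 6 |
| AUDIT-PC | 0 | 0 | 5 | 5 |

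The five follow-up marks for AUDIT-PC fall in the same positions as those for PHQ-9. Only the baseline cell differs.

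**2. Set the schedule against the outcome list.** Five follow-up marks agree with the protocol summary. They do not agree with 5.1.2 read literally, which would need a sixth mark at baseline.

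**3. Set the schedule against the model.** Section 8.3.3 treats baseline as a repeated observation of the outcome, not as a covariate. For AUDIT-PC at a given follow-up time, the model would need:

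- planned observations per participant: 2 (baseline and follow-up);
- observations available under the timeline: 1 (follow-up).

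With one observation per participant there is no baseline to account for. For a Gaussian outcome the random intercept also cannot be separated from residual error. A model over several follow-up visits could still carry a random intercept, but it would not account for baseline.

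**4. Size of the loss.** The protocol states no power, sample size or correlation for AUDIT-PC, so there is no figure to reproduce and the correlation r must be assumed. Accounting for baseline leaves a fraction of about 1 − r² of the outcome variance, so the standard error without baseline, relative to the standard error with it, is about 1/√(1 − r²).

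| r (assumed) | 1 − r² | Variance removed by baseline | SE ratio |
|---|---|---|---|
| 0.3 | 0.91 | 9% | 1.05 |
| 0.47 | 0.78 | 22% | 1.13 |
| 0.6 | 0.64 | 36% | 1.25 |
| 0.7 | 0.51 | 49% | 1.40 |

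The value 0.47 is the baseline to 12-week correlation that 8.1 gives for GAD7. It is shown only as a benchmark from the document, not as evidence about AUDIT-PC.

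**The case against.** **The outcome list may already be right.** Section 5.1.2 read literally includes baseline, and the word used in the summary for the follow-up measurements is compatible with an earlier one. On that reading the timeline merely lacks a mark. This stands in part: the defect is a contradiction within the protocol, not a settled decision to omit baseline. But 7.6 points staff to the timeline, so the contradiction has a practical consequence.

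**The table may be damaged.** In the text extracted from the PDF the header is broken and some marks look displaced. The second resource-use mark, for example, lines up with the last PHQ-9 mark, although 5.1.2 places that questionnaire at 26 weeks. The timeline is also not exhaustive: benzodiazepine use and panic symptoms have no row of their own. A lost mark cannot be fully excluded, and the laid-out table should be checked. Still, AUDIT-PC does have a row, and it matches its neighbours in every cell except baseline.

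**The comparison is randomised anyway.** This is correct. Follow-up AUDIT-PC scores can be compared between arms without bias from the missing baseline. A reader might infer that only unadjusted comparisons would remain, but 8.3.3 and 8.3.5 also provide for adjustment by the minimisation variables. What is lost is the outcome's own baseline.

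**Two stronger readings are not supported.**

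- Table 5 in 8.3.1 has the entry "Increased use of alcohol Treatment policy", and a reader might infer that this intercurrent event cannot be handled without a baseline alcohol score. Under treatment policy the week 12 GAD7 score is used whether or not drinking rose, so no reference value is needed. Section 8.3.6 confirms the approach: "The principal analyses will address a treatment strategy estimand, except death which will be while alive". At most, a rise from the pre-treatment level could not be described on this scale.
- A reader might also infer that the alcohol misuse exclusion in 3.2 cannot be applied. Section 3.3 establishes eligibility by phone screening, a baseline assessment and details from medical notes, so the exclusion does not depend on AUDIT-PC.

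**Conclusion.** The point holds as an inconsistency with a real but small consequence. Sections 5.1.2 and 5.2 disagree on whether AUDIT-PC is measured at baseline. If the timeline is followed, the analysis that 8.3.3 specifies for secondary outcomes cannot be carried out for AUDIT-PC.

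The cost is precision: a standard error about 5% to 40% larger than with baseline, on an assumed correlation of 0.3 to 0.7 that nothing in the protocol confirms. The between-arm comparison of follow-up scores remains valid. The primary outcome, its estimand and the sample size are untouched.

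The conclusion assumes that the empty baseline cell in the extracted timeline is also empty in the laid-out table, and that sites collect what the timeline shows. It is a minor point, worth acting on because the missing value cannot be obtained afterwards.

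**What to change.** Reconcile 5.1.2, 5.2 and 8.3.3:

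1. Add AUDIT-PC to the baseline column of the Participant Timeline, and state in 5.1.2 that it is measured at baseline and at each follow-up visit.
2. Use that score as the baseline observation in the mixed model, in the same way as for the other repeated outcomes.
3. Let participants already enrolled without a baseline AUDIT-PC contribute their follow-up observations only. A missing-baseline indicator is not needed, because baseline enters the model as an observation of the outcome and not as a covariate.

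The cost is one brief self-report scale at a visit that already takes place, and a protocol edit. If the laid-out timeline proves to have the baseline mark, only the wording needs tidying.
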